### 6. STUDY DESIGN AND METHODS OF DATA COLLECTION

This will be a feasibility study involving both qualitative and quantitative data developed in line with current guidance (19, 20). This feasibility study has been designed to establish the feasibility and acceptability of a future randomised controlled trial (RCT). It will involve pseudo-anonymised data collection from pregnant patients. This study will not involve an alteration to the standard care of enrolled patients.

Participants will undergo ultrasound with POCUS with a probe frequency of 3-5 MHz. The same probe model (Vscan Air CL, GE Voluson, available for routine clinical use for presentation scanning at LWH) will be used for all POCUS scans to limit variability in image quality. This model utilises a personal mobile device or tablet for image display and saves images which can be uploaded to a secure server. Measurements of fetal head circumference (HC), abdominal circumference (AC), and femur length (FL) will be taken with both devices and incorporated into the Hadlock EFW calculation. (21). Patients will also undergo ultrasound with a standard ultrasound machine (standard care). While performing the standard ultrasound, the PI will be blinded to the measurement value by covering the area of the screen where the measurement number appears with an opaque card. Both scans will be performed by the same sonographer (study PI) to limit inter-observer variability. The results of these scans will be examined using the statistical analysis as detailed below. Time taken to obtain measurements will be obtained for both methods and compared.

Clinical data will also be collected. This will consist of maternal and fetal details including maternal body mass index (BMI), antenatal risk factors, and the gestational age at the time of the scan.

Ultrasound findings and clinical measurements to be collected prospectively are illustrated in Appendix 1.

The qualitative component will address the primary objective and secondary objective 4. Participants will be asked to fill in an experience questionnaire following the ultrasounds. This questionnaire will evaluate their perception/satisfaction with the POCUS scan. Data for the qualitative component assessing acceptability will be obtained from the responses to the questionnaire. Participants will be provided either a paper-based or online questionnaire hosted at RedCap

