#### **POCUS versus SUM**

#### 5.2. Outcome

The primary outcomes will be the acceptability and feasibility of point-of-care ultrasound to patients. This will be assessed as:

- 1) The number of patients approached who agree to participate (objective 1)
- 2) The response rate to the questionnaire (objectives 2 and 3)
- 3) The number of patients willing to undergo POCUS scans in the future as determined by the questionnaire responses (objective 2)
- 4) The number of unblinding episodes that occur (objective 4)

The exploratory outcomes will investigate the reliability and validity of the point-of-care ultrasound device. This will be assessed as:

- 1) For categorical data, Kappa coefficients demonstrating 90% agreement or greater (objectives 1 and 2)
- 2) For numerical data, ICC 0.9 or greater (objectives 1 and 2)
- 3) For continuous data (fetal biometric measurements), high level of agreement with Bland Altman, defined as ≥95% of the differences between the two measurement methods fall within the clinically acceptable range of ±3 to ±7 mm, depending on gestational age (objectives 1 and 2)
- 4) The difference in the mean time taken to perform each type of scan (POCUS and SUM) (objective 3)
- 5) The number of patients in whom fetal assessment could not be performed (objective 2)
- 6) Data from the feasibility study will inform the sample size calculation for the full randomized controlled trial by providing estimates of outcome variability, effect size, and recruitment parameters necessary for a power analysis (objective 4)

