### 10.2 Data Analysis

### Data analysis and statistical analysis plan

Data arising from the questionnaires will be analysed in Microsoft Excel and will be reported using descriptive summary statistics, mean, medians, and counts (i.e. "54% of participants were satisfied with the POCUS scan").

Acceptability will be assessed using descriptive summary statistics, mean, medians, counts, and corresponding measures of variability.

Data will be analysed using SPSS (Statistical Package for the Social Sciences, IBM, Armonk NY).

The statistical methods have been chosen in collaboration with and at the advice of a University of Liverpool statistician ([name]) to ascertain agreement between the two methods of scanning (POCUS and SUM), and to enable appropriate statistical analysis of the proposed sample. Within each group we will use interclass correlation coefficients (ICC) and Spearman correlation coefficients (SCC) to check how closely the two methods agree by looking at the agreement between the paired measurements. Intraclass correlation coefficients measure how similar the measurements from the two methods are, indicating reliability or consistency for continuous variables. As the ICC approaches 1 (0.9 or greater), the greater the level of agreement. For this study, an ICC of 0.9 or greater will be considered a high level of agreement and indicate

increased reliability of the Vscan device.

To assess for difference in the scan duration, the mean scan time, median and interquartile ranges will be used. We will examine for correlation between the continuous variables of BMI and scan time with both POCUS and standard ultrasound. Calculation of a correlation coefficient will be performed with Spearman's correlation test.

Kappa coefficients measure agreement for categorical outcomes, such as assessments of fetal presentation or amniotic fluid levels. Values  $\leq 0$  indicate no agreement, 0.01–0.20 as none to slight, 0.21–0.40 as fair, 0.41–0.60 as moderate, 0.61–0.80 as substantial, and 0.81–1.00 as almost perfect agreement. These methods will be used to check for similarity within the methods (POCUS or SUM). This will ensure the measurements taken by the methods themselves are consistent.

Calculating the mean difference and 95% confidence intervals will provide estimate of any offset between two devices. Bland-Altman plots with limits of agreement will also provide a visual indication of the level of agreement between the two devices.

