# Measurements

POCUS: Fetal heartbeat, presentation, liquor volume (MVP), HC (mm), AC (mm), FL (mm), Umbilical Artery EDF, Placental location, EFW (g), Scan duration (HH:MM:SS)

SUM: Fetal heartbeat, presentation, liquor volume (MVP), HC (mm), AC (mm), FL (mm), Umbilical Artery EDF & PI, Placental location, EFW (g), Scan duration (HH:MM:SS

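### Scan order is not balanced and the standard scan includes an extra item, so the scan-time difference mixes device with order and workload; findings read from the image are not independent between scans

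*Protocol*

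**What the plan says.** Protocol section 6 (Study design and methods of data collection) gives one reason for using one operator: "Both scans will be performed by the same sonographer (study PI) to limit inter-observer variability". It describes the hand-held scan, then adds: "Patients will also undergo ultrasound with a standard ultrasound machine (standard care". On masking it says: "While performing the standard ultrasound, the PI will be blinded to the measurement value by covering the area of the screen". The cover is an opaque card over the place where the number appears. No cover is described for the hand-held device. The section does not say which scan comes first, whether order varies between patients, or when the hidden values are revealed.

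Appendix 1 (section 14.1, Measurements) lists the items for each device. For the hand-held device: "POCUS: Fetal heartbeat, presentation, liquor volume (MVP), HC (mm), AC (mm), FL (mm), Umbilical Artery EDF, Placental location, EFW (g), Scan duration (HH:MM:SS". The standard list is the same except for one item: "FL (mm), Umbilical Artery EDF & PI, Placental location, EFW (g), Scan duration (HH:MM:SS". In that list PI means pulsatility index. Each list ends with a single scan duration.

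In section 5.2, exploratory outcome 4 is: "The difference in the mean time taken to perform each type of scan (POCUS and SUM) (objective 3". Exploratory outcome 1 is categorical agreement by kappa, with a 90% criterion. Section 10.2 gives the summaries for time: "To assess for difference in the scan duration, the mean scan time, median and interquartile ranges will be used". It names fetal presentation and amniotic fluid level as examples of items for kappa.

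**The concern.** **Time.** Whoever scans a fetus for the second time already knows its lie, the placental site and where the planes are, so the second scan is likely to be quicker whichever device is used. The SUM scan also has one more item to obtain within its single timed period. Neither effect belongs to the device, yet both enter the comparison that answers exploratory objective 3 (efficiency). The background section presents speed as part of the case for hand-held devices, so the result will be read with interest.

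**Categorical agreement.** The card covers a read-out. Presentation, placental site, heartbeat and end-diastolic flow are read from the image, which stays in view. The operator has just established them on the first scan, so the second reading is not a fresh one. Agreement between two readings by someone who remembers the first tends to be too high.

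**Timing of the remedy.** Order, what is timed and when entries are made are settled at data collection. A later statistical analysis plan could not recover them.

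**Working it through.** **Plan's own figures.** Section 10.1: 60 × 3 = 180 patients and 180 × 2 = 360 scans. Both reproduce. There is no power calculation to reproduce.

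**Step 1: what the time difference estimates when the devices are equally fast.** Let e be the time for the extra SUM item, c the time saved on whichever scan is second, and q the share of patients scanned with POCUS first. Then

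apparent mean difference (SUM minus POCUS) = e − (2q − 1)c.

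The documents give none of e, c or q. Assume e and c each lie between 0.5 and 2 minutes.

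| Order | Expression | Range (min) |
|---|---|---|
| POCUS always first (q = 1) | e − c | 0.5 − 2 = −1.5 to 2 − 0.5 = +1.5 |
| Balanced (q = 0.5) | e | +0.5 to +2.0 |
| SUM always first (q = 0) | e + c | 0.5 + 0.5 = +1.0 to 2 + 2 = +4.0 |

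Over all orders the range is −1.5 to +4.0 minutes. If POCUS goes first, the order effect favours SUM and the extra item favours POCUS, so they partly cancel.

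**Step 2: would this be visible against sampling error?** The 95% CI half-width for a mean within-patient difference is 1.96 × SD/√n. Assume an SD of 2 to 5 minutes.

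- n = 180: 1.96 × 2/√180 = 0.29 and 1.96 × 5/√180 = 0.73 minutes.
- n = 60: 1.96 × 2/√60 = 0.51 and 1.96 × 5/√60 = 1.27 minutes.

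At n = 180, a 1-minute artefact would make the interval exclude zero with probability 0.77 (SD 5), 0.92 (SD 4) and more than 0.99 (SD 2 to 3).

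**Step 3: categorical agreement.** Take a binary finding with prevalence 0.2 and reading errors of 10% on the first scan and 2% on the second. Let the second reading repeat the first with probability r. All of these are assumptions.

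- r = 0: agreement = 0.90 × 0.98 + 0.10 × 0.02 = 0.884. The positive shares are 0.26 and 0.212, so chance agreement = 0.26 × 0.212 + 0.74 × 0.788 = 0.638, and kappa = (0.884 − 0.638)/(1 − 0.638) = 0.68.
- r = 0.5: agreement = 0.5 + 0.5 × 0.884 = 0.942; kappa = 0.845.
- r = 0.8: agreement = 0.8 + 0.2 × 0.884 = 0.977; kappa = 0.939.

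With smaller errors (5% and 1%), agreement is 0.941 at r = 0, so the 90% mark is passed without any carry-over. Kappa still rises, from 0.827 at r = 0 to 0.915 at r = 0.5. The direction is the same throughout; whether carry-over decides the result depends on the error rates.

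**Step 4: effect of the remedy on time.** With q = 0.5 the order term is zero for any c. With timing limited to the common items, e = 0. The expected difference under no device effect is then 0, apart from any time the card itself costs during SUM.

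**The case against.** **Single operator.** This is a reasoned choice, made to remove between-operator variation. That stands, and the point does not ask for a second sonographer.

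**Order.** The text is silent on order; it does not say that order is uncontrolled. The flow chart is not shown and may give a sequence. That stands as a matter of wording. But a fixed sequence would still tie device to order; only a randomised or balanced one would answer the point.

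**Spurious advantage for the hand-held device.** A reader might infer one from the longer SUM list. The documents do not support a direction. Section 6 describes the hand-held scan first, and if that is the order used, familiarity helps SUM. Both devices record end-diastolic flow, so the lists differ only by the pulsatility index. Nothing says that placing the card falls within the timed period.

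**Uncovered hand-held read-out.** A reader might infer that this breaks the blinding. It does not do so by itself. If SUM numbers stay hidden until both scans are finished, the operator cannot match one number to the other in either order. For the same reason the concern does not reach HC, AC and FL. Liquor volume is recorded as a measured pocket (MVP), whose SUM number may also be covered, although the visual impression is not.

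**Pairing.** A reader might infer that the time analysis ignores it. Section 10.2 specifies no unpaired interval or test for duration, and with complete pairs the difference in means equals the mean within-patient difference.

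**Weight.** Time and agreement are exploratory and no hypothesis testing is planned. Uptake, questionnaire response and willingness to be scanned again are unaffected. This lowers the severity; it does not remove the point.

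**Conclusion.** The point holds in limited form and should be fixed as a cheap improvement. Carried out as written, the plan yields a scan-time difference that cannot be attributed to the device. Its bias is unknown in size and net direction: −1.5 to +4.0 minutes under the assumed 0.5 to 2 minutes for each effect, against a half-width of 0.29 to 0.73 minutes at n = 180 under an assumed SD of 2 to 5 minutes. These minute values are illustrations, not figures from the protocol.

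Agreement on findings read from the image is likely optimistic. By how much depends on how often the second reading follows the first, which the study cannot measure. The numeric agreement analyses of HC, AC and FL are not implicated, on the condition that SUM values are not revealed until both scans are done. The protocol should state that condition.

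**What to change.** 1. Allocate scan order 1:1 from a pre-prepared list within each cohort (30 and 30 of 60), and record the order used.
2. Define the compared duration as time to the items common to both devices: heartbeat, presentation, MVP, placental site, HC, AC and FL. Time Doppler separately on each device.
3. Report the within-patient time difference with a 95% CI, adjusted for order.
4. Enter and lock the first scan's categorical findings before the second scan starts. This protects the first reading from later revision; it does not make the second reading independent.
5. State that SUM values are revealed only after both scans are finished.
6. Report kappa for presentation, placental site, heartbeat and end-diastolic flow as same-operator, non-independent agreement that is likely optimistic. Balanced order does not cure this, so all patients should stay in that analysis. True independence would need a second reader or masked reading of stored images.

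The cost is a sequence list, an extra time stamp, a small change in workflow and a few sentences of protocol text. The sample stays at 180 patients and 360 scans.

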#### 7. STUDY SETTING

This study will be a single-site study undertaken at LWH NHS Foundation Trust.

### 8. SAMPLE AND RECRUITMENT PARTICIPANT ENTRY

# 8.1 Eligibility Criteria

# 8.1.1 Inclusion Criteria

Pregnant patients attending Liverpool Women's Hospital for one or more of the following indications:

Routine assessment of the fetus due to maternal diabetes

Routine assessment of SGA fetus

Assessment of suspected SGA fetus on symphysis-fundal height measurement (SFH)Reduced fetal movements

Able and willing to provide informed written consent for participation in the study

Aged 18 years or above

#### 8.1.2 Exclusion Criteria

- Inability to provide informed consent
- Patients who have an abnormal CTG necessitating urgent delivery, or in established preterm labour

#### 8.2 Recruitment

### 8.2.1 Sample identification

We will publicise the study with posters and leaflets in the clinical waiting areas and we will encourage clinical staff interacting with these patients to offer participation in the study. Potential articipants will be approached by the clinical care team about participation, and if interestd referred to the research team who also work in the clinical care team.

#### 8.2.2 Informed Consent

The potential participant will be provided with the participant information leaflet, given time to read the leaflet and offered the opportunity to answer questions. If they wish to take part in the study, as the study is observational and will not impact their clinical care, they will be able to participate immediately. Potential participants will be offered a complimentary scan picture of their baby (position-permitting) as incentive to take part in the study.

#### 9. ADVERSE EVENTS

# 9.1 Definitions

Adverse Event (AE): any untoward medical occurrence in a patient or clinical study subject, including unfavourable and unintended signs, including abnormal laboratory results, symptoms or a disease associated with treatment.

Serious Adverse Event (SAE): any untoward and unexpected medical occurrence or effect that:

- · Results in death
- · Is life-threatening refers to an event in which the subject was at risk of death at the time of the event; it does not refer to an event which hypothetically might have caused death if it were more severe
- · Requires hospitalisation, or prolongation of existing inpatients' hospitalisation
- · Results in persistent or significant disability or incapacity
- · Is a congenital anomaly or birth defect

Medical judgement should be exercised in deciding whether an AE is serious in other situations. Important AEs that are not immediately life-threatening or do not result in death or hospitalisation but may jeopardise the subject or may require intervention to prevent one of the other outcomes listed in the definition above, should also be considered serious.

We do not anticipate any Adverse Events or Serious Adverse events resulting from this study due to its non-interventional nature. Ultrasound in pregnancy is safe and is used routinely. The handheld Vscan Air is used routinely at the Trust. Repeated ultrasounds in pregnancy have not been shown to be harmful to patient or fetus.

During routine growth scans performed for the indications given, fetal anomalies may be identified. While this is not an adverse event as its identification does not result from the study itself, any fetal anomalies identified during either the POCUS or standard ultrasound scans will be managed in accordance with LWH policy on reporting fetal anomalies and referral to the Fetal Centre for further assessment to be undertaken, if appropriate.

The risk of equipment failure is low, mainly due to the equipment being purchased within the last 24 months. Should device failure occur, an alternate device will be sought from LWH and repair requested from the manufacturer. There are multiple devices in use at the Trust for other purposes, and these are readily available the clinical research team.

# 9.2 REPORTING PROCEDURES

All adverse events should be reported. Depending on the nature of the event the reporting procedures below should be followed. Any questions concerning adverse event reporting should be directed to the Chief Investigator in the first instance.

### 9.2.1 Non-serious Adverse Events (AEs)

Adverse Events (AEs) are any untoward medical occurrence in a patient or clinical study subject, including unfavourable and unintended signs, including abnormal laboratory results, symptoms or a disease associated with treatment.

All such events, whether expected or not, will be recorded on a Case Report Form (CRF) and in the patient's medical notes.

# 9.2.2 Serious Adverse Events (SAEs)

Upon identification of an SAE the Principle Investigator should complete a study specific SAE form and sent to the Chief Investigator/Study Team within 24 hours. Relapse and death and hospitalisations for elective treatment of a pre-existing condition do not need reporting as SAEs.

Contact details for reporting SAEs

Please send SAE forms to: [name], [contact]

[contact] (Mon to Fri 09.00 – 17.00)

All SAEs should be reported to the sponsor and the REC, where in the opinion of the Chief Investigator, the event was:

- · 'related', i.e. resulted from the administration of any of the research procedures; and
- · 'unexpected', i.e. an event that is not listed in the protocol as an expected occurrence

Reports of related and unexpected SAEs should be submitted within 15 days of the Chief Investigator becoming aware of the event, using the HRA Non-CTIMP safety report to REC form. The Chief Investigator must also notify the Sponsor of all SAEs.

For University of Liverpool Ethics Committee approved studies please refer to

https://www.liverpool.ac.uk/intranet/media/livacuk/researchethics/reviewprocedures/Safety,reporting,and,ad verse,events,procedure.pdf (Section - Studies which require approval from the University's Sponsorship Committee)

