#### 3. RATIONALE FOR CURRENT STUDY

Increasing demand for ultrasound-based fetal growth surveillance is driven by the growing body of evidence implicating fetal growth restriction (FGR) and small for gestational age (SGA) as common causes of stillbirth, and a significant policy-based push toward reducing stillbirth rates at a national scale.

Patients at higher risk of FGR are identified following a risk assessment based on maternal characteristics and previous pregnancy outcomes, and are invited to undergo ultrasound assessment of fetal growth at regular intervals throughout the pregnancy (usually three to four weeks apart)(15). A cohort of these patients have risk factors that can make ultrasound assessment more challenging, including increased maternal body mass index (BMI) and diabetes leading to excess of amniotic fluid. Around one in 20 women who give birth in the UK have diabetes in pregnancy, either pre-existing or developed during the pregnancy. (16) Patients with diabetes and diagnosed SGA fetuses are required to attend more frequent scan appointments to ensure the fetal growth and wellbeing remains satisfactory (every two weeks or more if FGR is suspected). (17) Point-of-care devices are attractive to NHS services as they are more affordable than standard ultrasound machines, however it is unclear at present whether this is acceptable and feasible to deliver with training and image quality.

Patients presenting to the Maternity Assessment Unit (MAU) at or after 26 weeks of gestation with concerns regarding reduced fetal movements (RFM) in pregnancy represent a group with evolving risk for FGR. These patients are routinely offered a computerised CTG (cCTG) and an ultrasound scan assessment of fetal wellbeing comprising biometry, amniotic fluid volume assessment, and umbilical artery doppler studies. In our hospital, patients presenting with RFM at 39 weeks of gestation or greater are offered delivery via induction of labour or caesarean section and will only undergo ultrasound assessment in the event they decline delivery. As such, patients at 39 weeks or greater presenting with RFM will not be approached for this study.

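### Section 9.2.2 exempts death from SAE reporting, although the protocol's own definition and reporting rules make it a reportable SAE

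*Protocol*

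**What the plan says.** Four statements in section 9 bear on whether a death is reported.

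- Section 9.1 opens its definition with "Serious Adverse Event (SAE): any untoward and unexpected medical occurrence or effect that" and then lists the criteria. The first is "Results in death".
- Section 9.2 gives the general rule: "All adverse events should be reported".
- Section 9.2.2 sets the procedure: "Upon identification of an SAE the Principle Investigator should complete a study specific SAE form and sent to the Chief Investigator/Study Team within 24 hours". It adds: "The Chief Investigator must also notify the Sponsor of all SAEs". Events that the Chief Investigator judges both related to a research procedure and unexpected also go to the ethics committee within 15 days.
- The same section carries the exemption: "Relapse and death and hospitalisations for elective treatment of a pre-existing condition do not need reporting as SAEs".

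Nothing else in the protocol explains or limits the exemption for death. Section 9.1 anticipates no adverse events from the study and does not list death as an expected occurrence. Death is not an outcome in section 5.2, nor a data item in Appendix 1.

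**The concern.** The exemption takes out of SAE reporting the event that the definition puts first. The 24-hour form, notification of the sponsor and the ethics report all start from an event being handled as an SAE, so the exemption can switch off all three for a death.

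The other safeguards depend on that chain. Section 11.5 convenes no independent safety and data monitoring committee and leaves the assessment of participant safety to the study steering group. Section 12 keeps safety as the only ground for stopping early. If site staff followed the exemption, a report that no SAEs had occurred could be correct under section 9.2.2 and wrong under section 9.1.

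None of the study indications (diabetes, SGA, reduced fetal movements) is a condition described in terms of relapse. That suggests the sentence was carried over from another kind of study. This is an inference, and the contradiction does not depend on it.

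**Working it through.** No figure is involved, so the check is to run several kinds of death through the rules and see what each rule requires.

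**1. Unexpected maternal death, judged related to a study procedure.**
- Section 9.1: an SAE.
- Section 9.2: to be reported.
- Section 9.2.2, procedure: form within 24 hours, sponsor notified, ethics report within 15 days.
- Section 9.2.2, exemption: need not be reported as an SAE.
- Result: direct conflict, in the case for which the expedited route exists.

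**2. Unexpected maternal death, judged unrelated.**
- Section 9.1: an SAE.
- Section 9.2.2, procedure: form and sponsor notification. No ethics report, because the test of relatedness fails.
- Section 9.2.2, exemption: need not be reported as an SAE.
- Result: conflict. The exemption is also not needed to keep unrelated deaths out of ethics reporting, since the existing test already does so.

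**3. Narrow reading of the exemption.** Suppose the closing words about a pre-existing condition qualify death as well as hospitalisation. An unexpected death from a pre-existing condition still meets section 9.1 and is still exempt under section 9.2.2. The conflict covers fewer deaths but remains.

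**4. Expected death.** Section 9.1 is limited to unexpected occurrences, so an expected death could fall outside the definition and would then not conflict with it. The protocol lists no death as expected, and the exemption is not restricted to expected deaths, so this does not rescue the sentence.

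**5. Fetal death.** The adverse event definitions refer to a patient or study subject, and the participants are pregnant patients. The protocol does not say whether a stillbirth counts as an event of the participant. A contradiction between 9.1 and 9.2.2 is therefore not shown for fetal deaths. What is shown is that the scope of the definition is unclear.

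**Is there another route for a death?** Section 9.2.1 records adverse events on the case report form and in the medical notes, whether expected or not. It is headed as applying to non-serious events, so it is at best a partial route. It carries no 24-hour limit and no notification of the sponsor.

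**The case against.** The strongest reply is that little would be lost in practice.

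- The study is described as non-interventional. It has one scanning visit, follow-up is given as not applicable, and no birth or pregnancy outcome is collected. Most deaths after the scan would go unascertained whatever section 9.2.2 says.
- The exemption permits non-reporting and does not forbid reporting, so a cautious investigator could report anyway.
- The general rule in section 9.2, the case report form entry in section 9.2.1 and the steering group's review of all accumulating data give some chance that a death is seen.

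All of this stands as a limit on frequency and consequence. It does not settle which instruction governs, and it does not restore the three steps that the exemption removes.

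Two stronger readings are tempting. A reader might infer that every death would vanish from the sponsor's and steering group's view. The documents do not support that: the general reporting and recording text remains, the exemption has a narrower reading, and an expected death may lie outside section 9.1 anyway.

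A reader might also infer that the protocol exempts stillbirths in cohorts chosen for stillbirth risk. Section 3 does speak of evidence "implicating fetal growth restriction (FGR) and small for gestational age (SGA) as common causes of stillbirth" and says that patients with reduced movements "represent a group with evolving risk for FGR". That is context for the population. It does not make a fetal death a participant SAE. Section 3 also gives other reasons for interest in these groups, including difficulty of scanning and frequency of attendance.

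**Conclusion.** The contradiction is real and holds on either reading of the exemption. For an unexpected participant death, sections 9.1, 9.2 and the sponsor rule in 9.2.2 require reporting, while the exemption in 9.2.2 says that it is not needed. What is clearly at risk is the SAE form within 24 hours, notification of the sponsor and, for a related death, the ethics report.

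The size cannot be given as a number, because the documents contain no maternal or fetal death rate. Few such events are expected among 180 participants seen once for a low-risk procedure. The conclusion rests only on the wording of section 9 and on the absence of any text limiting the exemption. It leaves the feasibility and exploratory outcomes, the sample size and the analysis untouched. It still needs correcting, because it is an operative safety instruction at odds with the protocol's own definition for the gravest class of event.

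**What to change.** Reconcile sections 9.1, 9.2 and 9.2.2 so that the exemption no longer conflicts with the SAE definition. One way is to delete the words on relapse and death and keep the exemption for elective hospitalisation, if that is intended. If the aim was to spare the ethics committee reports of unrelated deaths, the test of relatedness and unexpectedness in section 9.2.2 already achieves it.

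As a secondary clarification, state in section 9.1 whether the SAE definition covers fetal as well as maternal events.

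The cost is a change to one sentence and one added clarification, submitted as an amendment where approval requires it. Given how few events are expected, the extra reporting work should be negligible.
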